# 10.3.2.2 Joints with limitation of range of motion

The assessment for LOM is made on 67 joints from the PRINTO/PRCSG standard joint examination. The sternoclavicular, acromioclavicular, and sacroiliac joints are excluded. Cervical, thoracic and lumbar joints are treated as a single composite joint; LOM in 1 or more of these 3 joints is counted as LOM for the composite joint. The number of joints with limitation of range of motion is the number of joints with Grade 1 for LOM and is weighted by the number of joints assessed:

$$LMC = \frac{67 * \sum_{i=1}^{n} JLM}{\sum_{i=1}^{n} JA}$$

where LMC=limitation of motion count, JLM=number of joints with limitation of range of motion, and JA=number of joints assessed. If more than 50% of the joints are not assessed for LOM, then the limitation of motion count will be set to missing.

The number of joints with limitation of range of motion and change from Baseline in number of joints with limitation of range of motion will be summarized (observed case) for every visit except the Final Visit.

Confidential Page 73 of 252

#### 10.3.3 Physician's Global Assessment of Disease Activity VAS

Descriptive statistics of the observed values and change from Baseline will be presented by visit.

Childhood Health Assessment Questionnaire

The CHAQ is an adaptation of the Health Access a questionnaire developed. The Investigator will assess the overall status of the study participant with respect to their

[figure not shown]
CHAO was developed specifically as a measure of function for children with juvenile RA and the population evaluated for the development of this questionnaire comprised study participants between ages 1 to 19 years old with JIA. The CHAQ is a parent/caregiverreported questionnaire and the recall period is "the past week." CHAQ data will be included regardless of the actual age of the study participant at the time the CHAQ was completed (eg. for ages > 19 years old).

The disability section of the CHAQ uses 30 questions (5-point Likert scale) to assess 8 domains of daily living, namely dressing and grooming, arising, eating, walking, hygiene, reach, grip, and activities. The scoring system used is: 0 = "without any difficulty", 1 = "with some difficulty", 2 = "with much difficulty", and 3 = "unable to do." In addition to the questions on activities of daily living, the CHAQ asks if any aids or devices or help from another person is needed to complete the specified activities. The question with the highest score determines the score for that domain. If aids or devices are used or help is needed to complete tasks in a certain area, a minimum score of 2 is recorded for the corresponding domain. Table 10-1 indicates which aids/devices correspond to each domain; any aids or devices other than those indicated below will not be considered in the calculation of domain scores. The scores for each of the 8 domains are averaged to calculate the Disability Index which yields a score from 0 representing "no disability" to 3 representing "very severe disability." A study participant must have scores for at least 6 of the 8 domains to calculate the Disability Index. If there is not a score for at least 6 of the 8 domains (ie 3 or more domains scores are missing), the Disability Index is considered missing.

Table 10-1: CHAQ Aids and Devices

Table 10-1: CHAQ Aids and Devices

The CHAQ will be completed by the parents/caregivers at Screening, Baseline, and every visit through the Early Discontinuation/EOT Visit. The same parent/caregiver should complete the questionnaire for each visit. The questionnaire should be checked by site personnel for completeness. The recall period is the past week. To eliminate discrepancies introduced by growth and development, parents/caregivers are asked to note only those difficulties that are caused by arthritis.

Descriptive statistics of the observed scores and change from Baseline will be presented by visit.

No additional analyses are planned to handle instances where the questionnaire is not completed by the same parent/caregiver at each visit. The person completing the CHAQ at each visit will be identified on the listing.

#### 10.3.5 Parent's Assessment of Arthritis Pain VAS

### 10.3.5.1 Updated Week 24 Interim Analysis

This data was only listed.

# 10.3.5.2 Final Analysis

The parent/caregiver is asked the following question "How much pain do you think your child has had because of his or her illness in the past week?" and then rates the severity on a 100 mm VAS where 0 = "no pain" and 100 = "very severe pain."

The Parent's Assessment of Arthritis Pain VAS will be completed at Screening, Baseline, and every visit through the Early Discontinuation/EOT Visit.

Descriptive statistics of the observed values and change from Baseline will be presented by visit.

No additional analyses are planned to handle instances where the Parent's Assessment of Arthritis Pain VAS is not completed by the same parent/caregiver at each visit. The person completing the Parent's Assessment of Arthritis Pain VAS at each visit will be identified on the listing.

#### 10.3.6 Parent's Global Assessment of Overall Well-Being VAS

For the Parent's Global Assessment of Overall Well-Being, the parent/caregiver is asked the following question "Considering all the ways that arthritis affects your child, rate how your child is doing on the following scale by placing a mark on the line." The parent/caregiver rates their response on a 100mm VAS where 0 = "very well" and 100 = "very poor."

The Parent's Global Assessment of Overall Well-Being VAS will be completed at Screening, Baseline, and every visit through the Early Discontinuation/EOT Visit.

Descriptive statistics of the observed values and change from Baseline will be presented by visit.

No additional analyses are planned to handle instances where the Parent's Global Assessment of Overall Well-Being VAS is not completed by the same parent/caregiver at each visit. The person completing the Parent's Global Assessment of Overall Well-Being VAS at each visit will be identified on the listing.

#### 10.3.7 C-reactive protein

The acute phase reactant CRP will be analyzed by 3 central laboratories.

Given the precision with which CRP values are reported, the following specific algorithms will be followed for each of the central laboratories:

- Cirion laboratory (lab='C\_RA0043\_1'): the minimum threshold of detection is 0.05mg/L; any CRP value reported as '0mg/L' will be set to 0.05mg/L for the summaries described in this section.
- LFK laboratory (lab='C\_RA0043\_2'): the minimum threshold of detection is 0.2mg/L. Due to LFK reporting conventions, CRP imputations will be as follows:
  - o when reported value is <0.000g/L, impute as 0.2mg/L
  - o when reported value is 0g/L, impute as 0.5mg/L
- LBM laboratory (lab='C\_RA0043\_3'): the threshold of detection is 0.5mg/L; any CRP value reported as '0mg/L' will be set to 0.5mg/L for the summaries described in this section.

CRP will be analyzed at Screening, Baseline, and every visit through the Early Discontinuation/End of Treatment Visit. The observed values and the percent change from Baseline of CRP will be summarized for each post-Baseline visit.

As the normality assumptions are not expected to be met for CRP, the geometric mean and the corresponding CV of the geometric mean will be summarized by visit for CRP and the percent change from Baseline of CRP values. The n, median, first quartile, third quartile, minimum, and maximum will also be presented.

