#### 2.2.3.3 Other efficacy and health outcomes variables

Other efficacy and health outcomes variables are:

- PedACR30, PedACR50, PedACR70, and PedACR90 response rates at every post Baseline visit, except Week 16 and Final Visit, as compared to Baseline.
- Change from Baseline in number of joints with active arthritis at every post-Baseline visit except Final Visit.
- Change from Baseline in number of joints with limitation of range of motion at every post-Baseline visit except Final Visit.
- Change from Baseline in Physician's Global Assessment of Disease Activity (visual analog scale (VAS)) at every post-Baseline visit except Final Visit.
- Change from Baseline in Childhood Health Assessment Questionnaire (CHAQ) at every post-Baseline visit except Final Visit.
- Change from Baseline in Parent's Assessment of Arthritis Pain (VAS) at every post-Baseline visit except Final Visit.
- Change from Baseline in Parent's Global Assessment of Overall Well-Being (VAS) at every post-Baseline visit except Final Visit.
- Percent Change from Baseline in C-reactive protein (CRP) at every post-Baseline visit except Final Visit.
- Change from Baseline in Juvenile Arthritis Disease Activity Score 71-joint (JADAS-71) at every post-Baseline visit except Final Visit.
- Percentage of study participants with Clinically Inactive Disease (CID) at every post-Baseline visit except Final Visit.
- Percentage of study participants with clinical remission on medication (CRM) at every post-Baseline visit from Week 24 onwards except Final Visit.
- Time (in days) to CID calculated from first dose of study medication.
- Time (in days) to CRM calculated from first dose of study medication.
- Change from Baseline in duration of morning stiffness (DMS) at every post-Baseline visit except Final Visit.
- Change from Baseline in Faces Pain Scale-Revised (FPS-R) (child-reported, ages 5 to 11 years), at every post-Baseline visit except Final Visit.

- Change from Baseline in JIA Pain VAS (acute and standard versions); at every post-Baseline visit except Final Visit

and Caregiver Work Productivity Survey responses

, and every post-Baseline visit except Final Visit.

Additional other variables

Additional variables that were covered under other variables that were specifically analyzed in the Updated Week 24 Interim Analysis only and were used for comparison purposes to support the regulatory submission include:

CZP plasma concentrations at Weeks 12 and 24

Anti-CZP antibody levels 

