Continuous variables will be summarized with the mean, standard deviation, median, minimum, and maximum. For CZP plasma concentrations and CRP, the geometric mean and geometric coefficient of variation (CV) will be presented.

Due to shifts in visit schedules per protocol amendments that were adopted at different times for different sites and study participants, some visits/ time points had very few study participants assessed. For categorical and continuous efficacy variables presented by visit/time point, if the visit/time point for the Any CZP Dose group contains 19 or fewer study participants with non-missing data, those visits/ time points will not be displayed in the efficacy tables or plotted in figures for Reduced CZP Dose, Original CZP Dose and Any CZP Dose groups. All information will appear in the listings.

Mean, standard deviation, and median will be displayed to 1 more decimal place than collected in the case report form (CRF). Minimum and maximum values will be displayed to the same level of precision as collected in the CRF. Percentages will be calculated using the number of study participants in the relevant population or subgroup as the denominator. Presentation of percentages will be to 1 decimal place. Percentages will not be presented if the frequency count is 0.

No formal statistical hypothesis testing will be performed. Ninety-five percent confidence intervals (CIs) for the percentage of responders will be calculated using the exact binomial method.

For certain laboratory parameter results that are collected as either "<XX.X" or ">XX.X", if descriptive statistics are calculated for the parameter, the XX.X will be used in the calculation

The classification of AEs occurring on the same date as a dose change will belong to the period of the dose change.

In addition, for other subgroup analyses (e.g. Baseline age group, concomitant MTX use, etc.), data will be generally presented by the specified subgroups pooling across all weight groups (with the exception of PK analyses which are specified in the corresponding sections).

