For joints with limitation of motion (LOM), it was stated in the protocol that the assessment of LOM would be made using 69 of the 75 joints from the standard PRINTO/PRCSG standard joint examination. In all SAPs since SAP Amendment 2, the assessment now utilizes 67 joints and this was according to an updated definition of LOM in the PRINTO/PRCSG assessment that was not available prior to the finalization of the protocol.

For CRP, summaries present the percent change from Baseline instead of the ratio to Baseline to aid in interpretation.

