### 8.1 **CZP** plasma concentrations

Only CZP plasma results analyzed using the ECLIA method will be summarized using the participants in the PK-PP set. CZP plasma concentrations are measured at Baseline, Weeks 1, 4, 12, 16, 17, 24, 32, 40, 48, every 24 weeks thereafter, the Early Discontinuation/EOT Visit, and the Final Visit; for study participants enrolled prior to Protocol Amendment 8, samples were not collected after implementation of Protocol Amendment 8. CZP plasma concentrations will be summarized by CZP dose (Original CZP Dose, Reduced CZP Dose) using geometric means, 95% CIs for the geometric mean, geometric CV, and the median, minimum and maximum concentrations.

The geometric CV will be calculated using the following formula:

$$geoCV(\%) = \sqrt{\exp(SD^2) - 1} * 100$$

where SD=standard deviation from the log-transformed data.

For the two CZP Dose groups, summaries at all available visits and plots of plasma concentration results will be produced separately by Baseline weight group, Baseline age group, ADAb participant status classification, ADAb titer classification (see Section 8.2) and, concomitant MTX use in combination with Baseline weight group.

Line-plots will be produced to summarize geometric mean (+/- 95% CI) plasma concentration over time. On each plot there will be separate plot lines for each subgroup category as described above. Plasma concentration will be plotted on both linear and semi-logarithmic scales.

In addition, spaghetti plots of CZP plasma concentrations over time will be produced for individual study participants, separately for each CZP dose group. Plots will be provided by Baseline age group, Baseline weight group, concomitant MTX use in combination with Baseline weight group. In each plot, different symbols/colors will be used to identify subgroup categories.

Concentrations below the limit of quantification of 320.0 ng/mL (0.32µg/mL) (BLQ) will be replaced by the LLOO divided by 2 for the calculation of descriptive statistics. The geometric

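### SAP Section 10.3.7 asks for a geometric mean and geometric CV of the percent change in CRP, two statistics that do not exist once any participant's CRP falls or is unchanged

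*SAP*

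**What the plan says.** SAP Section 10.3.7 names two CRP variables, the observed value and the percent change from Baseline, and applies the geometric statistics to both: the "geometric mean will be summarized by visit for CRP and the percent change from Baseline of CRP values", with the corresponding CV. It adds for the same summary: "The n, median, first quartile, third quartile, minimum, and maximum will also be presented".

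Section 3.1 sets the general rule: "For CZP plasma concentrations and CRP, the geometric mean and geometric coefficient of variation (CV) will be presented". Section 3.10 records the choice of scale: "For CRP, summaries present the percent change from Baseline instead of the ratio to Baseline to aid in interpretation". Section 2.2.3.3 lists the variable among the other efficacy and health outcomes variables: "Percent Change from Baseline in C-reactive protein (CRP) at every post-Baseline visit except Final Visit".

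The only geometric CV formula in the SAP is in Section 8.1, for plasma concentrations. It is the square root of exp(SD²) - 1, times 100, "where SD=standard deviation from the log-transformed data".

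Section 10.3.7 also replaces CRP results reported as zero by small positive values that depend on the laboratory. For one laboratory, for instance, "any CRP value reported as '0mg/L' will be set to 0.05mg/L for the summaries described in this section".

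**The concern.** A geometric mean is the exponential of the mean of the logs, and the geometric CV uses the SD of the logs. Both require every value to be above zero. Percent change in CRP is below zero for each participant whose CRP falls and exactly zero for each whose CRP is unchanged. A fall is the direction in which an effective anti-inflammatory treatment should move CRP, so the undefined values would be expected to be common.

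The ratio to Baseline is always positive once zero results have been replaced, and geometric statistics suit it. Section 3.10 sets the ratio aside, while Section 10.3.7 asks for geometric statistics on the percent change. Nothing in the SAP says that they are to be computed on the ratio and back-transformed, or how zero and negative changes are to be handled.

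At stake are two rows at each summarised post-Baseline visit. They would be blank, or they would show a rise in CRP from a selected minority while the median in the same table showed a fall.

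**Working it through.** The SAP prints no figure for this summary, so there is none to reproduce. The check applies the definitions.

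**Definitions.** For participant i, with b_i the Baseline CRP and v_i the CRP at the visit:
- percent change p_i = 100 x (v_i - b_i)/b_i
- ratio r_i = v_i/b_i, so p_i = 100 x (r_i - 1)
- geometric mean of x = exp(mean of ln x_i)
- geometric CV of x = 100 x sqrt(exp(SD²) - 1), with SD that of ln x_i (Section 8.1)

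ln p_i exists only if r_i > 1, that is, only if CRP rose. The zero-replacement rules make b_i and v_i positive, so ln r_i always exists, but they do not change the sign of p_i. If Baseline and visit both carry the same substituted value, p_i is exactly 0 and its log is minus infinity.

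**Five invented participants.** Baseline 20, 10, 8, 5, 15 mg/L; visit 4, 2, 8, 10, 1.5 mg/L.
- p = -80, -80, 0, +100, -90%.
- As written: ln p is undefined for three values and minus infinity for one, so there is no geometric mean and no CV.
- Keeping positive values only: one participant is left and the result is +100%.
- On the ratio: r = 0.2, 0.2, 1, 2, 0.1; ln r = -1.609, -1.609, 0, 0.693, -2.303; mean = -4.828/5 = -0.966; geometric mean ratio = exp(-0.966) = 0.381; geometric percent change = (0.381 - 1) x 100 = -61.9%. The SD of ln r is 1.255, so the geometric CV of the ratio = 100 x sqrt(exp(1.575) - 1) = 196%.

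**Size under assumed distributions.** The SAP gives no CRP distribution, so the inputs are assumptions: r log-normal with geometric mean g and log-SD s. The share falling is Φ(-ln g / s). For g = 0.3 and s = 0.8 this is Φ(1.204/0.8) = Φ(1.505) = 93%. The last column is the geometric mean of p over participants with p > 0, by numerical integration.

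| g | s | True geometric change | Share with a fall | Geometric mean if only rises are kept |
|---|---|---|---|---|
| 0.3 | 0.8 | -70% | 93% | +25% |
| 0.3 | 1.5 | -70% | 79% | +85% |
| 0.5 | 0.8 | -50% | 81% | +35% |
| 0.5 | 1.5 | -50% | 68% | +108% |
| 0.7 | 0.8 | -30% | 67% | +44% |
| 0.7 | 1.5 | -30% | 59% | +129% |

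The last column is positive in every row. It must be, because only rises enter it. The stronger the fall in CRP at a given s, the fewer participants the statistic describes.

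**The case against.** The best defence is that a sensible reading exists. Showing a percentage to help interpretation is compatible with computing a geometric mean ratio and printing it as (ratio - 1) x 100, and the zero-replacement rules make that computable. Section 10 says CRP was among the variables presented in the Updated Week 24 Interim Analysis, so a program probably exists and may do exactly this. That is fair as far as it goes, but the SAP does not state it, Section 3.10 removes the ratio, and the document does not show which calculation was used.

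Four stronger readings are tempting and not supported.
- That the whole CRP table fails. It does not. Geometric statistics for observed CRP are valid, and so are n, median, quartiles, minimum and maximum for percent change. A median near the true fall would stand beside any spurious positive figure and expose it.
- That PedACR or JADAS-71 is affected because CRP is a component. Sections 10.2 and 10.3.8 derive both from each participant's own CRP, not from these group statistics.
- That the protocol planned a geometric mean and CV of the ratio. Section 3.10 shows only that it named a ratio to Baseline.
- That the output will certainly be wrong in sign. That follows only if non-positive values are dropped; if the software returns missing, the rows are blank and mislead nobody.

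**Conclusion.** The instruction is wrong as written. A geometric mean and geometric CV of percent change do not exist for a group in which anyone's CRP falls or stays the same. This follows from the definitions and needs no assumption about the data.

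The defect is confined to those two rows, for a descriptive variable listed under other efficacy variables. Section 10.1 states that there is no primary efficacy variable and Section 3.1 that there is no formal hypothesis testing, so no decision hangs on these rows. Severity is moderate.

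The range of about +25% to +129%, against a true -70% to -30%, is illustrative. It rests on the assumed log-normal ratio, on the chosen geometric means and log-SDs, and on non-positive values being dropped.

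**What to change.** Amend Section 10.3.7, with a matching clause in Section 3.10, to state that for change in CRP:
- the geometric mean and geometric CV are computed on the ratio visit/Baseline, after the zero-replacement rules;
- the geometric percent change is reported as (geometric mean ratio - 1) x 100, with the CV labelled as that of the ratio;
- raw percent change is summarised only by n, median, first and third quartiles, minimum and maximum.

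This keeps the percentage scale that Section 3.10 wants. It costs a sentence or two of text and one derived variable. One further small task is to check how the CRP change rows in the Updated Week 24 Interim Analysis were computed and, if they differ, to note the difference in the clinical study report.

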# 10.3.8 Juvenile Arthritis Disease Activity Score 71-joint

The JADAS-71 is a composite disease activity score based on a 71-joint count and includes the measures:

- Physician's Global Assessment of Disease Activity VAS normalized to a 0 to 10 scale by dividing the score by 10
- The Parent's Global Assessment of Overall Well-Being VAS normalized to a 0 to 10 scale by dividing the score by 10
- The number of joints with active arthritis (0 to 71, weighted by the number of joints assessed)
- CRP normalized to a 0 to 10 scale as follows: if CRP is expressed in mg/dl, any values above 10 are converted to 10. If expressed in mg/L, the value will be first divided by 10 and then any values above 10 will be converted to 10. Values below the minimum threshold for the method used for CRP determination are converted to 0 (see Section 10.3.7 for minimum CRP thresholds).

The JADAS-71 is calculated as the linear sum of scores of the 4 components with a total score range of 0 to 101. If any component of the JADAS-71 is missing, the JADAS-71 will be set to missing for the corresponding visit.

Descriptive statistics of the observed composite scores and change from Baseline will be presented by visit (except at Final Visit).

#### 10.3.9 Clinically Inactive Disease

# 10.3.9.1 Updated Week 24 Interim Analysis

This data was only listed.

### 10.3.9.2 Final Analysis

A study participant will be considered to be in CID at a given point in time if they meet all of the following criteria:

- No joints with active arthritis: based upon both (1) a "No" response to the question "Has the subject experienced any of the following since the last visit Joint(s) with active arthritis?", and 0 joints with active arthritis at the current visit
- No fever, rash, serositis, splenomegaly, or generalized lymphadenopathy attributable to JIA: based upon a "No" response to the question "Has the subject experienced any of the following since the last visit Fever, rash, serositis, splenomegaly, or generalized lymphadenopathy attributable to JIA?"
- No active uveitis as defined by the Standardization of Uveitis Nomenclature Working Group: based upon a "No" response to the question "Has the subject experienced any of the following since the last visit Active uveitis as defined by the Standardization of Uveitis Nomenclature Working Group?"
- CRP within normal limits in the laboratory where tested or, if elevated, not attributable to JIA: based upon a "No" response to the question "Has the subject experienced any of the following since the last visit Elevated CRP levels attributable to JIA?"
- Physician's Global Assessment of Disease Activity score of best possible on the scale used (ie, 0mm on the 100mm VAS): based upon VAS score at current visit

Duration of morning stiffness of ≤15 minutes: based upon duration of morning stiffness at current visit

The 6 criteria above will be used to derive CID. If any of the 6 criteria cannot be assessed due to missing data, the study participant will be assumed not to have achieved derived CID at the corresponding visit.

Derived CID will be assessed at every post-Baseline visit except the Final Visit.

The n and percentage of study participants with derived CID will be summarized for each post-Baseline visit. The exact 95% CI for the percentage will also be presented.

Time to initial derived CID in days will be calculated as date of first visit where derived CID is achieved – date of first dose of study medication + 1 day. Time to initial derived CID in days will be presented using Kaplan-Meier product limit estimation. Study participants that discontinue without achieving derived CID will be censored at the time of discontinuation; ongoing study participants that have not achieved derived CID at the time of interim analyses (Week 24 and other interim analyses) and the final analysis will be censored at the time of the last available assessment. The median and 95% CI for the time to initial derived CID will be presented. The 95% CI for the median will be based on the method of Brookmeyer and Crowley. Kaplan-Meier product limit survival estimates of the cumulative proportion of study participants with derived CID (1 minus the product limit estimate of the proportion of study participants without derived CID) will also be presented. Kaplan-Meier plots of time to CID will be presented overall and by Baseline weight group.

Both summaries of derived CID and time to derived CID will be provided as well as listed.

